Unblinded pharmacist, also identified as Mixer, will keep records of the treatment assigned to each subject in the unblinded pharmacy binder. Access to this pharmacist binder will be limited to the unblinded pharmacist.

Blinding for Clinical Evaluators

To minimize assessment bias, clinical evaluators (data analysts and physicians) will be trained on how to maintain blinding to treatment as best as possible. "Best as possible" means that blinding will be maintained unless an adverse event or serious adverse events occurs that requires unblinding the physician, which is determined by the medical monitor or DSMB.

Training includes review of the process of blinding, describing who will be responsible for assigning product for the appropriate group, labels that will be used to identify subjects but not treatment group, and the process that should be followed if an adverse event occurs, triggering review by medical monitor and/or DSMB.

Prior and Concomitant Medications

Concurrent and prior medications (up to one week before the screening visit) should be recorded in the subject's medical history at the screening visit. This list of concomitant medications may be updated if necessary, at the following visits.

It is important to ask the subject about the start and end date of the current and prior medications, if the subject does not remember the specific date or month, it is recommended to include the approximate year to give an estimate of how long the patient has been taking the medication.

Trial Procedures

The trial includes a up to 28 days screening period, a 32-week Treatment Period and a 20-week Safety Follow-up Period. All periods are associated with evaluations and procedure that must be performed at specific time points as represented in Table 3 Schedule of Assessments.

Trial Schedule of Assessments.

Table 3 Schedule of Assessments.

	Visit 1	Visit 2	Visit 3	Visit 4	Visit 5	Visit 6	Visit 7	Visit 8	Visit 9										
Visit Names Window Period Visit Weeks	Screening Up to 28 days N/A	INF 1 + 7 days 0	INF 2 + 7 days 4	INF 3 + 7 days 8	INF 4 + 7 days 16	INF 5 + 7 days 24	INF 6 + 7 days 32	Follow Up + 7 days 42	EOS + 7 days 52										
										Informed Consent	•								
										Demographics	•								
Medical History	•	•	•	•	•	•	•	•	•										
Concomitant Medications	•	•	•	•	•	•	•	•	•										
Eligibility Criteria	•	•																	
Vital Signs	•	•	•	•	•	•	•	•	•										

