A clinical laboratory abnormality should be documented as an adverse event. Any adverse event that results in hospitalization or prolonged hospitalization should be documented and reported as a serious adverse event unless specifically instructed otherwise in this protocol. Any condition responsible for surgery should be documented as an adverse event if the condition meets the criteria for an adverse event. All unresolved adverse events should be followed by the investigator until the events are resolved, the subject is lost to follow-up, or the adverse event is otherwise explained

Serious Adverse Event

Adverse events are classified as serious or non-serious. A *serious adverse event* is any AE that is:

- fatal
- life-threatening
- requires or prolongs hospital stay
- results in persistent or significant disability or incapacity
- a congenital anomaly or birth defect
- an important medical event

Important medical events are those that may not be immediately life threatening but are clearly of major clinical significance. They may jeopardize the subject and may require intervention to prevent one of the other serious outcomes noted above. All adverse events that do not meet any of the criteria for serious should be regarded as *non-serious adverse events*. Serious adverse events that are still ongoing at the end of the study period must be followed up to determine the final outcome. Any serious adverse event that occurs after the study period and is considered possibly related to the study treatment or study participation should be recorded and reported immediately.

Adverse Event Reporting Period

The study period during which adverse events must be reported is normally defined as the period from the initiation of any study procedures to the end of the study treatment follow-up. For this study, the study treatment follow-up is defined as approximately 20 weeks following the last administration of study treatment.

Stopping Rules

Infusion Stopping Rules

Study treatment infusion will be stopped if a least one of the following events occur:

- 1. Allergic reaction as evidenced by severe dyspnea, bronchospasm, or hypoxia after the product has been administered intravenously.
- 2. Patient verbally decline the treatment at any moment prior, or during the infusion.
- 3. Hyperpyrexia develops after infusion administration begins (core body temperature greater than or equal to 104°F).

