• To investigate the safety and efficacy of intravenous infusions of HB-adMSCs vs Placebo in patients with Parkinson's disease as determined by improvements in Quality of Life, estimated by the MDS UPDRS assessment. (Time frame: Baseline to Weeks 4, 8, 16, 24, 32, 42 and 52). A battery of statistical tests will be applied, where suitable and applicable. Tests will include the report of parametric or non-parametric statistical tests, with the corresponding p-values, presented in pair-wise manner, as well as contingency tables, representing answers in their native form.	 Change from Baseline in Total MDS-UPDRS Part II, only at Week 52 Number of treatment-emergent Adverse Event (TEAEs) during 52 week period Number of serious Adverse Events (SAEs) during the period of 52 weeks Number of AEs of special interest includes thromboembolic events, peripheral events defined as thromboembolism of the extremities, infections and hypersensitivities Change from baseline in clinical parameters, measured at the end of the study (52 weeks): Physical examination Electrocardiogram (ECG) Pulse Systolic blood pressure Body weight BMI Change from baseline in laboratory assessments at the end of the study (52 weeks):

Protocol Number: HBPD03

Date: 18-Apr-2023 Version: 2.0 Hope Biosciences Statistical Analysis Plan Status: Final

Objectives	Endpoints
	o Biochemistry
	 Haematology
	 Urinalysis
Secondary Objectives	Secondary Endpoints
To evaluate the safety and efficacy of intravenous infusions of HB-adMSCs vs Placebo in patients with Parkinson's disease based on	Change from Baseline in MDS- UPDRS Total score, at all the timepoints collected, during the period of study (52 Weeks)
changes in disease assessments and dosage of medications. (Time frame: Baseline to Weeks 4, 8, 16, 24, 32, 42 and 52).	 Change from Baseline in Total MDS- UPDRS Part I, at all the timepoints collected during the period of study (52 Weeks)
	 Change from Baseline in Total MDS- UPDRS Part II, at all the timepoints collected during the period of study (52 Weeks)
	 Change from Baseline in Total MDS- UPDRS Part III at all the timepoints collected during the period of study (52 Weeks)
	 Change from Baseline in Total MDS- UPDRS Part IV, at all the timepoints collected during the period of study (52 Weeks)
	 Change from Baseline in Total Neuro- Quality of Life Assessments scores (Neuro-QOL), at all the timepoints collected during the period of study (52 Weeks)

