8.1. Adverse Events Analyses

AEs will be coded using the most recent version of the Medical Dictionary for Regulatory Activities (MedDRA).

A treatment emergent adverse event (TEAE) is defined as an event that has onset date on the first day of exposure or after the first day of exposure to infusion treatment, and no later than 3 days after the last day of infusion treatment. AEs with missing start and/or stop dates will be assumed to be treatment emergent.

Treatment adverse events (TAE) are summarised descriptively, whereas non-TEAEs are presented in listings. TAE data will be displayed in terms of the number of subjects with at least one event (N), percentage of subjects with at least one event (%) and the number of events E.

Summaries of TAE and of serious AEs will be presented as an overview, including all AEs, AEs listed by severity, serious AEs, AEs by relation to treatment, action taken after AEs occurred and treatment advised, and the outcome of AEs.

Furthermore, summary tables based on system organ class and preferred terms are made for:

- All TAEs
- Serious AEs
- AEs leading to withdrawal of study

Individual adverse events will be listed.

The details of the planned displays are in Error! Reference source not found..

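### SAP 8.1 lets a missing stop date alone make an adverse event treatment-emergent, even when its known onset lies outside the TEAE window

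*SAP*

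**What the plan says.** SAP 8.1 sets the TEAE window by onset alone. It opens with "onset date on the first day of exposure or after the first day of exposure to infusion treatment" and closes with "and no later than 3 days after the last day of infusion treatment". The next sentence gives the missing-date rule: "AEs with missing start and/or stop dates will be assumed to be treatment emergent". Treatment-emergent events are summarised descriptively, "whereas non-TEAEs are presented in listings".

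The SAP's table of objectives and endpoints names among the primary endpoints "Number of treatment-emergent Adverse Event (TEAEs) during 52 week period".

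The protocol collects adverse events over a longer span than the TEAE window. Under Adverse Event Reporting Period it is "the period from the initiation of any study procedures to the end of the study treatment follow-up", and "the study treatment follow-up is defined as approximately 20 weeks following the last administration of study treatment". Under Trial Procedures: "The trial includes a up to 28 days screening period, a 32-week Treatment Period and a 20-week Safety Follow-up Period".

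Three other places bear on the point:

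- Protocol Table 3 marks AE and SAE assessment from Visit 2 onwards, not at Visit 1.
- Protocol, Physical Examinations, sends pre-existing conditions diagnosed during screening to medical history. It also requires clinically significant findings discovered after consent to be recorded as adverse events.
- SAP 10.1.2 treats data as missing when a requested field is left blank, and says that answers such as not applicable are not missing.

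**The concern.** Whether an event is treatment-emergent depends on when it began. A stop date helps to place the onset only when it falls before first exposure, because the event must then have begun before treatment. A missing stop date says nothing about onset. The rule nevertheless makes a missing stop date sufficient, and it does not require the start date to be missing, partial or inside the window.

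An event that is still ongoing ordinarily has no stop date, and the protocol expects some events to be unresolved at study end. Events with a known onset outside the window and no stop date are therefore foreseeable. For these events, entry into the TEAE tables would depend on how long the event lasted and whether the stop-date field was filled in. TEAE count is a primary safety endpoint in a trial with 12 participants per arm, so a few such events are visible in the tables.

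**Working it through.** **Inputs**

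- Infusions at Weeks 0 to 32 and end of study at Week 52, with a visit window of ±7 days (Protocol Table 3).
- Screening of up to 28 days (Protocol, Trial Procedures).
- Study Day 1 is the day of the first dose (SAP 10.1.1).
- The TEAE window closes 3 days after the last infusion day (SAP 8.1).
- 12 participants per arm (Protocol, Investigational Product Assignment).

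**The plan's own figure.** Follow-up after the last infusion is 52 − 32 = 20 weeks, which agrees with the protocol's approximately 20 weeks.

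**Nominal study days for a participant who receives all six infusions**

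- Last infusion: 32 × 7 + 1 = Day 225.
- TEAE window closes: 225 + 3 = Day 228.
- Week 52: 52 × 7 + 1 = Day 365.
- On-study days after the window: 365 − 228 = 137 days, or 137/7 = 19.6 weeks. As a share of on-study days this is 137/365 = 37.5%.
- If only the Week 52 visit moves by ±7 days, the span is 130 to 144 days.
- With up to 28 screening days added: (137 + 28)/(365 + 28) = 165/393 = 42% of the period.

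**The rule applied literally.** An event is a TEAE if the start date is missing, or the stop date is missing, or onset falls on Days 1 to 228.

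| Known onset | Resolved | Stop date missing |
|---|---|---|
| Day −10 | not TEAE | TEAE |
| Day 100 | TEAE | TEAE |
| Day 228 | TEAE | TEAE |
| Day 229 | not TEAE | TEAE |
| Day 300 | not TEAE | TEAE |
| Day 360 | not TEAE | TEAE |

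The two columns differ only for onset outside the window. If a missing stop date no longer triggers the rule, they agree on every row.

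**How many late events could be caught.** The documents give no event rates or durations, so this is an illustration on assumptions. Let onset be uniform over T = 137 days and duration exponential with mean m. The share still ongoing at Week 52 is (m/T) × (1 − exp(−T/m)):

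- m = 7 days: 5%
- m = 30 days: 22%
- m = 90 days: 51%

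**Effect of one event.** If it is the participant's only counted event, the arm's incidence moves by 1/12 = 8.3 percentage points. If the participant has another TEAE, incidence does not move and the event count rises by one.

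**The case against.** The strongest objection is that ongoing need not mean missing. SAP 10.1.2 excludes answers such as not applicable from missing data, and SAP 8.1 summarises the outcome of adverse events, so resolution status is collected. If the case report form has an ongoing entry that makes the stop date not applicable, the rule might never reach ongoing events. This stands as a real uncertainty, because the form is not in the documents. It does not rescue the rule: neither document mentions such an entry or exempts ongoing events, and a stop date that is simply left blank is caught on any reading.

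The pre-dose side is also narrow. Table 3 starts AE assessment at Visit 2, and conditions diagnosed in screening become medical history. That stands. Some pre-dose events remain possible, because the reporting period begins with the first study procedure and clinically significant findings after consent are adverse events.

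A third objection is that counting doubtful events as emergent is cautious. It is when onset is unknown. When onset is known and outside the window, nothing is in doubt, and the rule contradicts the definition just before it.

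Finally, for late-onset events the rule over-includes, which moves the count towards the 52-week endpoint; it is the 3-day cut-off that removes those events. This is correct. However, the rule restores only the unresolved ones, so it is no substitute for settling the cut-off.

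**Conclusion.** The missing-date rule is wrong as written, because a missing stop date alone overrides a known onset date. The consequence for ongoing events assumes that they appear with a missing stop date. On that assumption, events with known onset before first exposure, or on nominal Days 229 to 365, are classified by whether they resolved. The later period is the material one; the pre-dose contribution is probably small. The size cannot be estimated from the documents beyond 8.3 percentage points of descriptive incidence for each participant whose only counted event is affected.

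A reader might infer more than this, and the documents do not support it:

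- *That ongoing events in general count while identical resolved ones do not.* Onset inside the window makes an event a TEAE either way.
- *That pre-treatment events are attributed to the product.* Treatment emergence is a label for timing, and relation to treatment is summarised separately in SAP 8.1.
- *That the rule biases the comparison.* It is the same in both arms, and SAP 8.1 summarises adverse events descriptively without a between-arm test. Small counts can still shift, in either direction.
- *That events are concealed.* Individual adverse events are listed.

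This is a clear drafting error in a primary safety endpoint. It should be corrected, but it does not undermine the trial.

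**What to change.** In SAP 8.1, delete *and/or stop* from the missing-date sentence and state:

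> Treatment emergence is determined by onset date. An AE with a missing or partial start date is assumed treatment-emergent unless the known part of the start date shows onset outside the TEAE window, or the stop date is before first exposure. A missing stop date (ongoing event) does not affect classification.

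The partial-date clause refers to the whole window, so that a partial date clearly after the window is treated like a full one.

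At the same time, reconcile the 3-day cut-off with the primary endpoint's 52-week period, since the two describe different sets of events.

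The cost is one revised passage in the SAP and about one line of derivation code, with no new data. There is a small downside: if the 3-day cut-off is kept, late-onset ongoing events move from the TEAE tables to the listings, further from the 52-week endpoint. That is why the two changes belong together.

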8.2. Clinical Laboratory Analyses

Laboratory evaluations including the analyses of Biochemistry laboratory tests (includes Comprehensive Metabolic Profile), Hematology laboratory tests (Complete Blood Count

Statistical Analysis Plan

(CBC) and Coagulation Panel) and Urinalysis. The details of the planned displays are in **Error!** Reference source not found...

All laboratory parameters, including numerical urine analysis parameters will be summarised descriptively. Categorical urine analysis results will be summarized using count and percentage based on subjects. Differences in safety Lab parameters after the treatment was applied are tested using the Mann-Whitney U (or Wilcoxon Rank-Sum) Test.

Distribution of laboratory test results will be presented using scattered box-plot.

Change from baseline laboratory measurements available at post-baseline at scheduled measurements will be analyzed using Repeated Measures ANOVA. The model will include treatment, visits as fixed factors. The within subject factor is visit and with 2 levels (Weeks 24 and 52). The between-subjects factor is treatment (HB-adMSCs 200MM or Placebo).

Results of urine pregnancy test will be listed only in the individual subject data listings.

Individual laboratory evaluations will be listed. In addition, a listing containing individual subject laboratory values outside the normal reference ranges will be provided separately.

Data recorded at unscheduled assessments will not be included in tables and figures but will be listed.

8.3. **Other Safety Analyses**

The analyses of non-laboratory safety test results, including physical examination and vital signs. The details of the planned displays are presented in Error! Reference source not found..

Physical Examination and Vital signs will be summarized using count and percentage based on subjects. The vital signs based on visit and change from baseline will be summarized using descriptive statistics.

Individual Vital signs, Physical Examination evaluations will be listed.

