	Placebo: Saline Solution 0.9%						
	Dose: N/A						
	Route: Intravenous						
	Regimen: Weeks 0, 4, 8, 16, 24 and 32.						
Duration of administration	1 hour						
Laboratory Samples.	Screening, Week 0, 24 and 52.						
Visits by Weeks	Screening						
	Week 0 – Infusion 1						
	Week 4 – Infusion 2						
	Week 8 – Infusion 3						
	Week 16 – Infusion 4						
	Week 24 – Infusion 5						
	Week 32 – Infusion 6						
	Week 42 – Follow Up.						
	Week 52 – End of Study						

"A Randomized, Double-Blind, Single Center, Phase 2, Efficacy and Safety Study of autologous HB-adMSCs vs Placebo for the Treatment of Patients with Parkinson's Disease"

Introduction

Objectives

Primary Objective:

• To investigate the safety and efficacy of intravenous infusions of HB-adMSCs vs Placebo in patients with Parkinson's disease as determined by improvements in Quality of Life as measured by the MDS UPDRS assessment. (Time frame: Baseline to Weeks 4, 8, 16, 24, 32, 42 and 52).

Secondary Objective:

• To evaluate the safety and efficacy of intravenous infusions of HB-adMSCs vs Placebo in patients with Parkinson's disease as, determined by changes in disease assessments and dosage of medications. (Time frame: Baseline to Weeks 4, 8, 16, 24, 32, 42 and 52).

Endpoints

Primary Endpoints

The safety and efficacy endpoints of this study will be evaluated by assessing changes from Baseline to Weeks 52 in the following:

- Changes in MDS-UPDRS Part II from Baseline to Week 52. Motor Aspects of Experiences of Daily Living (M-EDL), including speech, saliva and drooling, chewing and swallowing, eating tasks, dressing, hygiene, handwriting, doing hobbies and other activities, turning in bed, tremor, getting out of bed, a car, or a deep chair, walking and balance and freezing.
- Incidence of treatment-emergent Adverse Event (TEAEs) and serious Adverse Events (SAEs).
- Incidence and risk of AEs of special interest (serious or nonserious), including thromboembolic events, peripheral events defined as, thromboembolism of the extremities, also infections and hypersensitivities.
- Clinically significant changes in laboratory values, vital signs, weight and physical examination results.

Secondary Endpoints

The safety and efficacy endpoints of this study will be evaluated by identifying changes from Baseline to Weeks 4, 8, 16, 24, 32, 42 and 52 in the following:

- Changes in MDS-UPDS Part I, III, IV, or total score.

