A repeat measure mixed model will be used to assess within-subject changes from baseline. correction for multiple comparisons will be employed for post-hoc comparisons. Parkinson's assessment scores (i.e., MDS-UPDRS) at screening and infusion 1 (before treatment) will be averaged and treated as a baseline. Averaging is performed to minimize sources of variance (i.e., patient condition, assessors) and particularly to establish a reliable baseline from which to establish changes.

Data Handling Case Report Forms (CRF)

As used in this protocol, the term CRF should be understood to refer to either a paper form or an electronic data record or both. Reports received by the site, or from the central laboratory should be printed, retained as source documentation and signed by the principal investigator, indicating which values are considered clinically significant and to be reported as AEs if applicable.

Source data is all information, original records of clinical findings, observations, or other activities in a clinical trial necessary for the reconstruction and evaluation of the trial. Source data are contained in source documents

Changes in the Conduct of the Clinical Trial Protocol Amendments

Any change to the protocol will need to have a protocol amendment submitted to the IND, and FDA and IRB must agree prior to proceeding.

Deviations from the Protocol

Deviations from the protocol should not occur. If safety deviations occur, the principal investigator must inform the Monitor, and the implications of the deviations must be reviewed and discussed. Any deviation must be documented in the protocol deviation log. In addition, each deviation must include a description of the deviation, the relevant dates (start and stop), and the action taken. All deviation reports and supporting documents must be kept in the Investigator Site File and in the Trial Master File.

Premature Clinical Trial Termination

Both the Study Investigator and Sponsor have the right to terminate the clinical trial at any time. Should this become necessary, the procedures will be agreed upon after consultation between the two parties. In terminating the clinical trial, the Sponsor and the Study Investigator will ensure that adequate consideration is given to the protection of the best interests of the study participants. Regulatory authorities and IRB will be informed.

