5.6 General Considerations

Unless otherwise stated, all hypotheses will be tested at 0.95% confidence interval (p = 0.05, two-sided test, when applicable). In other words, statistical test will look for the difference (either better results or worse results), rather than focusing solely on efficacy. All continuous measurements will be summarised descriptively at each visit, followed by treatment, using observed data.

Summary of continuous variables will be presented using the total number of participants (N), Mean, Standard Error of mean (SE), Standard Deviation (SD), Median and Range (Minimum and Maximum). The categorical variables will be presented using the number and the percentage of subjects who have provided the defined categorical answer.

For measurements obtained during course of time, mean values will be plotted to explore the trends. Observed data will be used as the basis for plotting data along with standard error (SE) or Standard Deviation (SD) represented as bars, if not otherwise specified.

A non-parametric Mann-Whitney U Test (or Wilcoxon Rank-Sum Test) will be applied on primary and secondary efficacy endpoints to test the significance of the effects of the treatment by comparing median values.

For measurements performed over time, median values will be plotted to explore the trends. Observed data will be used as the basis for plotting the data along with Inter Quartile Range (IQR) used as bars, if not otherwise specified.

A parametric, repeated measurements ANOVA will be applied as a sensitive analysis to test the significance of the effects of the treatment.

Change from baseline safety Lab measurements will be analyzed using a repeated measurements ANOVA to test the significance of the effects of the treatment.

Presentation of results from a statistical analysis model will include the estimated means caused by treatment effects, using Adjusted Mean. HB-adMSCs 200MM vs Placebo group will be compared.

For all endpoints analyzed statistically, estimated mean treatment differences will be presented together with two-sided 95% confidence intervals and p-values.

All safety evaluations will be presented using Safety analysis set while the efficacy analysis

Individual safety and efficacy parameters will be listed.

will be presented using Efficacy analysis set.

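### The protocol's primary endpoint of clinically significant laboratory changes becomes group-level change from baseline in the SAP, with no stated by-arm count of affected patients

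*SAP*

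**What the plan says.** **Protocol.** The last of the four Primary Endpoints is "Clinically significant changes in laboratory values, vital signs, weight and physical examination results". The section on case report forms has the principal investigator sign each laboratory report, "indicating which values are considered clinically significant and to be reported as AEs if applicable". Another primary endpoint is "Incidence and risk of AEs of special interest (serious or nonserious"), covering thromboembolic events, infections and hypersensitivities. Laboratory samples are taken at screening and Weeks 0, 24 and 52, and AEs are reported until about 20 weeks after the last administration.

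**SAP.** The table of objectives and endpoints gives the laboratory endpoint as "Change from baseline in laboratory assessments at the end of the study (52 weeks"). The idea of clinical significance is gone. Section 5.6 states: "Change from baseline safety Lab measurements will be analyzed using a repeated measurements ANOVA to test the significance of the effects of the treatment". Section 8.2 adds: "Differences in safety Lab parameters after the treatment was applied are tested using the Mann-Whitney U (or Wilcoxon Rank-Sum) Test". For individual patients, section 8.2 plans box-plots with points, individual listings, and "a listing containing individual subject laboratory values outside the normal reference ranges will be provided separately". Unscheduled laboratory values are kept out of tables and figures and only listed.

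Section 8.1 ends the treatment-emergent window 3 days after the last infusion and puts AEs outside it in listings. Its tables by organ class and preferred term cover all treatment AEs (taken here to mean treatment-emergent ones), serious AEs, and AEs leading to withdrawal. The SAP's own endpoint table, in contrast, counts treatment-emergent AEs over 52 weeks.

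**The concern.** The protocol asks how many patients had a laboratory change that a physician considered important. The SAP asks whether the distribution of change differs between arms. These are different questions. If a cell product harms a few patients, the harm may appear as a large abnormality in one or two of 12, and a comparison of medians or means does little to reveal it. If the SAP is followed as written, the report will present a different endpoint under the primary label. Some patients with an abnormality will then enter no by-arm count. AEs of special interest, also primary, have a similar gap: section 8.1 names no table that groups them by arm.

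**Working it through.** The documents give no power, effect size or event rate for laboratory endpoints, so there is no planned figure to reproduce. The check has two parts.

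**1. Which abnormalities reach a by-arm count through the AE tables?** The protocol requires laboratory abnormalities to be recorded as AEs, so this is the only route that the SAP text describes.

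- Week 24 draw (Infusion 5): inside the treatment-emergent window, so counted.
- Week 52 draw: the last infusion is nominally at Week 32. (52 − 32) × 7 = 140 days, and 140 − 3 = 137 days after the window closes. A new non-serious event with complete dates is only listed. This affects one of the two post-baseline draws.
- Unscheduled draws: the protocol gives safety laboratory sampling as a reason for such visits, but the values are only listed. An AE recorded from them is counted if its onset is inside the window.

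**2. How far can the group tests stand in for a count?** Inputs: 12 per arm (protocol, randomization section) and two-sided 0.05 (SAP 5.6). Assumption: k HB-adMSCs patients have values far above all others, and everyone else in both arms shares one normal distribution.

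- *Mann-Whitney.* Expected U = 12k + (12 − k) × 12/2 = 72 + 6k. The null mean is 72 and the null SD is √(12 × 12 × 25/12) = 17.32, so z = 6k/17.32. The rejection rate comes from 20,000 simulated trials with the exact test.
- *ANOVA.* A two-sample t test on one value per patient stands in for the between-patient test, simulated with a shift of 10 SD.
- *Fisher exact test* of k/12 against 0/12: p = 2 × C(12,k)/C(24,k). For k = 3 this is 2 × 220/2024 = 0.217.

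| k | 0 | 1 | 2 | 3 | 4 | 5 | 6 |
|---|---|---|---|---|---|---|---|
| Mann-Whitney p at expected U | – | 0.73 | 0.49 | 0.30 | 0.17 | 0.083 | 0.038 |
| Mann-Whitney, % of trials with p < 0.05 | 4.4 | 4.7 | 7.0 | 12.4 | 21.6 | 34.9 | 55.1 |
| t test at 10 SD, % with p < 0.05 | 5.0 | 0.7 | 3.5 | 22.5 | 73.2 | 98.5 | 100 |
| Fisher p | – | 1.00 | 0.478 | 0.217 | 0.093 | 0.037 | 0.014 |

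If the k values are equal and so large that other variation is negligible, t tends to √(11k/(12 − k)) on 22 df: 1.00, 1.48, 1.91 and 2.35 for k = 1 to 4 (p = 0.33, 0.15, 0.07, 0.03). This is a limit, not a general bound. With a 10 SD shift, 3 of 12 still reach significance in 22.5% of trials.

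**3. What would a count add?** With a true rate of 20% in the active arm and 0% on placebo, the chance of the 5 or more cases that Fisher needs is 7%. The chance of at least one case to display is 1 − 0.8¹² = 93%.

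**The case against.** A reader might infer that extreme abnormalities cannot show up as a difference between arms. The documents do not support that. Section 5.6 reports minimum and maximum by visit and treatment, section 8.2 plans box-plots and an out-of-range listing, and with 12 per arm a few extreme values will be seen. Week 24 abnormalities recorded as AEs are counted by arm, and serious AEs have their own summary. This stands, and it narrows the gap. But none of these displays reports the protocol's endpoint: being out of range is not the same as being judged clinically significant, and a listing is not a count.

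A reader might also infer that the rank test is simply the wrong test and that comparing proportions would detect the harm. It would not: Fisher needs 5 of 12 against 0. The weakness comes from 12 patients per arm. What is missing is the definition and the tabulation.

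It can be argued that Week 52 events are counted after all, because section 8.1 treats AEs with a missing start or stop date as treatment-emergent. Read literally, an event still ongoing would qualify. But inclusion would then depend on whether a stop date had been entered, and an event with both dates would still only be listed.

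It would also be tempting to count the chance signals expected from many unadjusted laboratory tests. The documents do not give the number of analytes or of tests per analyte, so no figure is claimed here.

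Finally, the planned displays are cited through a reference that does not resolve, so a by-arm table of laboratory abnormalities or AEs of special interest may exist there. That limits certainty about what is absent. It does not change the SAP text, which redefines the endpoint.

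**Conclusion.** The point holds in this form. One of several primary safety endpoints in the protocol is restated in the SAP as group-level change from baseline, and no readable SAP text defines a clinically significant laboratory change or counts patients with one by arm. Non-serious, fully dated abnormalities first found at Week 52 would be listed only, and so would unscheduled values. The planned group tests are nearly insensitive to one or two extreme patients in 12: Mann-Whitney rejects in 5% and 7% of trials, against 4% with none. These rates rest on the assumed data model, with 12 evaluable patients per arm and extremes in one arm only. The 137 days assume six infusions on the nominal schedule. The mismatch between the two documents rests on neither assumption.

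**What to change.** **SAP 8.2.** Restore the protocol endpoint: number and percentage of patients by arm with at least one post-baseline value judged clinically significant by the investigator, at any scheduled or unscheduled visit to Week 52, with an exact confidence interval for the difference. Add a table of shifts from baseline to worst value for each analyte, using all values. The rule that takes the last non-missing measurement at a visit could otherwise hide an abnormal first result. Label the change-from-baseline tests as descriptive or exploratory. Align the SAP endpoint table with this.

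**SAP 8.1.** Add a by-arm table (patients, percentage, events) of AEs of special interest over 52 weeks. Reconcile the 3-day treatment-emergent window with the 52-week period in the SAP endpoint table and the 20-week AE follow-up in the protocol. Repair the reference to the planned displays, and if these tables are already there, cite them in the text.

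**Cost.** SAP wording and a few tables. The investigator's judgements are recorded on signed source reports, and the documents do not say that they are entered in the database, so some data entry may be needed, done before unblinding. No new measurements are required.
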